## 5.15. Adverse Events

### 5.15.1. Definitions

An adverse event (AE) is defined as any untoward medical occurrence occurring in a clinical trial. An AE does not necessarily have a causal relationship with the device. A device-related AE can be any unfavorable and unintended sign, symptom, or disease temporally associated with the use of a study device, whether or not related to the device.

**For the purposes of this study, only AEs that are possibly, probably, or definitely related to the study ulcer, study treatment, and/or study procedures are to be recorded.** All events starting or worsening beginning at SV2 through Treatment Visit Week 13 and unscheduled visits will be collected. Follow-up treatment and evaluation should continue until the AE has resolved or until 2 weeks after the final visit, whichever occurs first.

AEs not related or unlikely related to the study treatment, study ulcer and/or study procedures are not to be recorded for this study.

A Serious Adverse Event (SAE) is defined as any AE that:

- Results in death

- Is life threatening (the subject is at immediate risk of dying from the adverse experience)
- Requires subject hospitalization or prolongs existing hospitalization
- Results in persistent or significant disability/incapacity
- Is a congenital anomaly/birth defect
- Important medical events that may not result in death, be life-threatening, or require hospitalization may be considered a serious adverse device effect when, based upon appropriate medical judgment, they may jeopardize the subject or subject and may require medical or surgical intervention to prevent one of the outcomes listed in this definition.

For the purposes of this study, only SAEs that are possibly, probably, or definitely related to the study ulcer, study treatment, and/or study procedures are to be recorded. All events starting or worsening after the first randomized treatment through Treatment Visit Week 12 will be collected. Follow-up treatment and evaluation should continue until the SAE has resolved or until 2 weeks after the final visit, whichever occurs first.

SAEs not related or unlikely related to the study treatment, study ulcer and/or study procedures are not to be recorded for this study.

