### 5.15.3. Adverse Event Relatedness Assessments

All AEs will be assessed for their relatedness to the study device or the procedures. An AE is considered device-related if there is a reasonable possibility that the device caused or contributed to the event. Information that “reasonably suggests” a causal relationship includes any information such as professional, scientific or medical facts and observations or opinions that would reasonably suggest that a device has caused or may have caused or contributed to the event. If the chance that a device may have caused or contributed to an event is very remote or very unlikely, the event should be considered not related to the device.

AE causality will be assessed using the guidelines outlined in Table 2.

Table 2: Adverse Event Causality Categories

Relationship	Comment
Definitely	This category applies to those AEs which the investigator feels are incontrovertibly related to the study treatment , study ulcer or study procedures. An AE may be assigned an attribution of definite if or when (must have all three): 
 
a) It follows a reasonable temporal sequence from application of the device.
 
b) It could not be reasonably explained by the known characteristics of the subject’s clinical state, environmental or toxic factors or other modes of therapy administered to the subject.
 
c) It follows a known response pattern to treatment with the device.
 

Probable	
This category applies to those AEs which, after careful medical consideration at the time they are evaluated, are felt with a high degree of certainty to be related to the device. An AE may be considered probable if or when (must have three):
 
 
a) It follows a reasonable temporal sequence from application of the device.
 
b) It could not readily have been produced by the subject’s clinical state, environmental or toxic factors, or other therapies administered to the subject.
 
c) Disappears or is decreased upon removal of the device.
 
d) It follows a known response pattern to treatment with the device.
 

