### 5.17.2. PriMatrix Application Training

All investigators and Sub-investigators who will be applying PriMatrix for the trial will be trained on the use of the study device, PriMatrix, for the management of DFUs, along with other study-related procedures.

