## 8.1. Treatment Groups

The following treatment groups will be assessed:

Group	Description
Control (SOC)	Moist ulcer dressings consisting of 0.9% sodium chloride gel plus secondary dressings and an appropriate off-loading/protective device. (See Section 5.11 for full information)
Active Treatment	PriMatrix Dermal Repair Scaffold plus secondary dressings to maintain a moist wound healing environment and an appropriate off-loading/protective device. (See Section 5.17 for full information)

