12.7. Adverse Events

Adverse Events will be coded using the MedDRA Medical Dictionary. AE's are defined as events with an onset after screening visit 1. Treatment Emergent AE's (TEAE) are defined as events with an onset on or after the randomized treatment. TEAEs will be summarized by treatment group, System Organ Class, and preferred term. The following TEAE summaries will be provided:

- TEAEs by severity grade
- TEAEs by relationship to study treatment.

In addition, separate summaries of Serious Adverse Events, and Adverse Events resulting in discontinuation of study treatment will be presented.

The safety population will be used for the safety analyses. Subjects will be counted only once for subject-based analysis. If the same event changes in severity for a subject, the worst severity will be reported.

An Adverse Event is considered treatment emergent if (1) it was not present at Screening Visit 1, and it is not a chronic condition that is part of the subject's medical history; or (2) it is present at Screening Visit 1 or as part of the subject's medical history, but the severity or frequency increases during treatment.

Treatment-emergent adverse events (TEAE) will be summarized for each treatment group by body system and preferred term. The severity of all adverse events will be determined by the investigator's judgment and classified as mild, moderate or severe.

Treatment groups will be compared with respect to the incidence of Adverse Events (all and TEAEs) and the proportion of subjects withdrawing from the study for Adverse Events by reason of withdrawal. Comparisons will be made overall, by body system and by preferred term and will be further categorized by severity and by study device relationship.

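### The last SAE criterion in protocol 5.15.1 turns important medical events into an undefined device effect, so whether such an event is serious can depend on how a site reads it and on the arm

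*Protocol*

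**What the plan says.** Protocol 5.15.1 opens its list with "A Serious Adverse Event (SAE) is defined as any AE that" and gives six bullets. Five complete that sentence: death, threat to life, hospitalization, disability and congenital anomaly. The sixth is a free-standing sentence: "Important medical events that may not result in death, be life-threatening, or require hospitalization may be considered a serious adverse device effect when", in medical judgement, they may put the subject at risk and may need intervention to prevent one of the listed outcomes.

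The following paragraph sets the recording scope: "only SAEs that are possibly, probably, or definitely related to the study ulcer, study treatment, and/or study procedures are to be recorded". That scope covers both arms.

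The study device is named in protocol 5.17.2, where those applying it "will be trained on the use of the study device, PriMatrix, for the management of DFUs". Protocol 8.1 describes control as "Moist ulcer dressings consisting of 0.9% sodium chloride gel plus secondary dressings and an appropriate off-loading/protective device".

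On relatedness, the first paragraph of 5.15.1 says a device-related AE can be any unfavorable event "temporally associated with the use of a study device, whether or not related to the device". Protocol 5.15.3 says: "An AE is considered device-related if there is a reasonable possibility that the device caused or contributed to the event".

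In the analysis, SAP 12.7 states that "separate summaries of Serious Adverse Events, and Adverse Events resulting in discontinuation of study treatment will be presented". Protocol 8.12.5 says the same, and protocol 8.12.4 has all safety parameters summarized by treatment.

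**The concern.** Seriousness should be decided by what happened to the subject, and relation to the device should be judged separately. The sixth bullet merges the two. It does not say that an important medical event is an SAE. It says the event may be put in a different class whose name presupposes that the device caused it.

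This criterion exists for events that meet none of the other five. Protocol 5.15.4 lists ulcer infection or abscess, osteomyelitis and amputation among the events that commonly occur in this population. If one of these does not lead to admission and meets no other criterion, the sixth is the only way it can count as serious. The trial is open-label (protocol 3 and 8.5), so the investigator applying a device-worded, permissive criterion knows whether the subject has the device. At stake is whether the SAE summaries count the same kind of event in both arms.

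**Working it through.** No arithmetic applies. The check is whether anything in the documents settles what the sixth bullet means.

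1. **The term.** Serious adverse device effect is defined in neither document. Protocol 5.15.4 defines only the unanticipated adverse device effect, which is a different concept.
2. **The device.** Protocol 5.17.2 identifies it as PriMatrix. Control subjects may wear a sponsor-provided off-loading device, but so may PriMatrix subjects, and protocol 12.3 lists the device, the SOC supplies and the off-loading device as separate products. The off-loading boot therefore gives the word no meaning in control.
3. **The SAP.** Its abbreviation list refers the reader to section 5.1 for the SAE definition. SAP 5.1 is the study flow chart, and protocol 5.1 is informed consent. Neither supplies a definition.
4. **Severity.** The note in protocol 5.15.2 says that a severe AE is not necessarily serious, so the severity grade does not stand in for the criterion.

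Now take a recordable AE that is an important medical event and meets none of the first five criteria. Three readings of the sixth bullet are open:

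| Reading | PriMatrix arm, attributed to PriMatrix | PriMatrix arm, not attributed | Control arm |
|---|---|---|---|
| A. Separate class, not an SAE | not an SAE | not an SAE | not an SAE |
| B. Serious when a device effect | SAE | not an SAE | not an SAE |
| C. Ordinary SAE criterion | SAE | SAE | SAE |

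Readings A and B follow the words; C follows the position of the bullet in the list. Under A and B, an event not attributed to PriMatrix is never serious by this route. Only B treats the arms differently. A mixture of A and C across sites makes the counts inconsistent but does not by itself favour an arm, since randomization is 1:1 within center (protocol 8.4).

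The two statements on relatedness also conflict. Under 5.15.1, timing alone can make an AE device-related. Under 5.15.3, there must be a reasonable possibility that the device caused or contributed to it, and an event with only a very remote chance of this is not related. A site using the looser sentence under reading B could treat almost any later event in a PriMatrix subject as a device effect.

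**The case against.** The strongest reply is that the bullet sits under a heading sentence covering any AE, refers back to the outcomes in the same definition, and is followed by a recording scope that includes the study ulcer. On that view the device term is a drafting slip, and sites would apply reading C in both arms. This is plausible, and it stands to this extent: different treatment of the arms is possible, not established.

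A reader might infer more than the documents support.

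- **That PriMatrix subjects have six routes to an SAE and control subjects five.** This holds only under reading B, and then only for events attributed to PriMatrix. Under A both arms have five; under C both have six.
- **That a spurious excess of SAEs can be put in percentage points.** The documents give no SAE rate and no share of events managed without admission. The 207 subjects in SAP 11.1.1 are the primary efficacy population; safety is analysed on the safety population (SAP 10.3), whose size is not given.
- **That the Fisher comparison in SAP 13.2.3 is distorted.** That endpoint is conditional on relation to the device by its own wording, and rewording the sixth bullet does not change that.
- **That every listed ulcer complication treated without admission depends on the sixth criterion.** An amputation may meet the disability criterion.

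It is also fair to say that causality is assigned from Table 2 in 5.15.3, and that no analysis is shown to use the looser sentence in 5.15.1. The contradiction remains in the text. Finally, the protocol disagrees on which SAEs are recorded at all: related only in 5.15.1, all in 5.15.5 and 8.12.4, with only device- or procedure-related ones to be reported in the special instructions of 5.15.5. That is a separate matter which this change does not settle, and those sections need reconciling too.

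**Conclusion.** The point holds as a fault in an operative definition. As written, an important medical event that meets none of the other five criteria and is not attributed to PriMatrix is not an SAE, and in control no such event can be. Sites taking the bullet as an ordinary criterion would classify the same event as serious. The by-arm SAE summaries can therefore depend on the reading adopted and, under one reading, on the arm.

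This rests on the study device being PriMatrix and on no other section repairing the wording; both were checked above. Which reading sites used is not known, so neither the size nor the direction of any effect on reported counts can be stated. The contradiction between 5.15.1 and 5.15.3 on device-related AEs is certain from the text, though its practical effect is not shown.

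**What to change.** Make two wording changes in protocol 5.15.1.

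1. In the sixth SAE bullet, replace the words from *may be considered* to *when* with: *are considered a serious adverse event, in either arm and regardless of relation to the device, when*. The rest of the bullet stays.
2. Delete the third sentence of the first paragraph, the one containing "temporally associated with the use of a study device, whether or not related to the device", so that 5.15.3 holds the only definition of a device-related AE. Delete the whole sentence: striking only the qualifier *device-related* would leave a second general AE definition tied to device use beside the arm-neutral one that opens the section.

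The cost is a site memo and a few more events classified as SAEs. No treatment, visit or sample size changes. SAP 10.4 records that enrollment was ended early, so events already classified would stay as they are unless the memo also asks sites to check recorded AEs against the corrected criterion.

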#### 5.15.5. Adverse Event Reporting Procedures

All AEs related to study treatment, study ulcer and/or study procedures spontaneously reported by the subject and/or in response to an open question from study personnel or revealed by observation, physical examination or other diagnostic procedures will be evaluated.

At each visit, after the subject has had the opportunity to spontaneously mention any problems, the investigator should inquire about AEs by asking standard questions such as:

- “Have you had any (other) medical problems since your last visit / assessment?”
- “Have you taken any new medicines since your last visit /assessment?”

The following AEs will be recorded on the appropriate eCRF:

- All AEs related to study treatment, study ulcer and/or study procedures occurring after the 1st randomization treatment.

- All SAEs occurring after signing of ICF through the last study visit

When possible, signs and symptoms indicating a common underlying pathology should be noted as one comprehensive event.

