**Special instructions for SAEs**

Study centers are instructed to report SAEs to Integra within 5 business days of becoming aware of the SAE.

SAEs must be reported by the investigator to Integra by completing the eCRF SAE Form. Only SAEs that are considered causally related to the study device or procedures need to be reported. Reporting will utilize the standard AE eCRF. Note: Follow-up information on the SAE may be requested by the sponsor.

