### 6.1. Screening Phase

#### 6.1.1. Screening Visit 1 (SV1)

At SV1, the following data will be collected, or activities performed:

1. Informed Consent and HIPAA Authorization
  - Note: Once the ICF and HIPAA authorization are signed, the screening assessments/activities identified must be completed within a **30-day window** from the date of ICF signature. Further, all screening assessments/procedures must be completed on the same day, and that date will constitute the first day of the screening phase.
2. Review of Inclusion and Exclusion criteria for eligibility
3. Demographics
4. Medical history, medications, and non-study treatments
5. Physical exam (including vital signs, height and weight)
6. Vascular perfusion
7. Perform ulcer assessments
8. Photograph the study ulcer pre-debridement
9. Perform ulcer measurements pre-debridement
10. Perform sharp debridement of the study ulcer
11. Photograph of the study ulcer post-debridement
12. Perform ulcer measurements post-debridement
13. Apply SOC treatment to the ulcer (see Section 5.11 for specific application processes)

14. Discuss treatment compliance with the subject
15. If appropriate, apply the off-loading/protective device and discuss compliance with its use
16. Document applicable Concomitant Medications noted by the subject or seen within the subject's medical records (see Section 5.14 for information on which medications require documentation).

*\*Remember to schedule the next visit for SV2, 7±3 days from SV1.*

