13.2.3. Other Variables

Discontinuations

The difference between treatments, both overall and for each primary reason, will be compared by using a 2-sided Fisher's exact test.

Demographic and Baseline Characteristics

Comparisons between treatment groups of continuous variables will be made by using a one-way analysis of variance with treatment as a factor. For categorical variables, the Fisher's exact test will be used. All tests will be 2-sided and performed at the 0.05 level of significance.

Time-to-Event Data

Time-to-event endpoints including time-to-complete-wound-closure/healed will be evaluated using the Kaplan-Meier method. The log-rank test will be used to compare the distributions between two treatment groups, stratified by the ulcer size (1 cm² to ≤ 3 cm² vs. > 3 cm² to 12 cm²).

Rate of Wound Closure, as Assessed by Computerized planimetry

Analysis of Covariance (ANCOVA) will be used to compare the rate of wound closure (as defined in section 13.2.2 for the two treatment groups. The stratification factor, ulcer size at the time of randomization, will be used in this analysis. Other covariate, as outlined in section 11.4, may also be incorporated in the model, if their presence is statistically significant (i.e. p-value ≤ 0.05).

Safety Data

The primary safety endpoint for this study is any severe device-related complication where relationship to the device was assessed by the clinical event committee possible, probably, or definite. Fisher's exact test will be used to compare incidence rates of serious device-related complications as well as for any device-related complication, and for specific complications between the treatment group and the control group.

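### Protocol 5.15.1 and 5.15.5 give contradictory SAE recording rules, and data recorded under 5.15.1 cannot support the stated all-SAE safety endpoint; SAP 12.7 and 13.2.3 also need reconciling

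*Protocol*

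**What the plan says.** Protocol 5.15.1 restricts recorded SAEs to those at least possibly related to the ulcer, the treatment or the procedures, and adds that "SAEs not related or unlikely related to the study treatment, study ulcer and/or study procedures are not to be recorded for this study". Its SAE window is: "All events starting or worsening after the first randomized treatment through Treatment Visit Week 12 will be collected". For AEs in general the same section has a wider window: "All events starting or worsening beginning at SV2 through Treatment Visit Week 13 and unscheduled visits will be collected".

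Protocol 5.15.5 lists what goes on the eCRF and includes "All SAEs occurring after signing of ICF through the last study visit", with no condition on relatedness. The special instructions that follow say: "Only SAEs that are considered causally related to the study device or procedures need to be reported". They also say: "Reporting will utilize the standard AE eCRF".

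The safety endpoint in the Protocol synopsis and in SAP 3.4 is related AEs plus all SAEs. The synopsis safety analysis text, Protocol 8.12.4 and SAP 12.6 say all SAEs will be recorded. Protocol 8.2.4 is less specific and mentions only AEs and SAEs.

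SAP 12.7 defines a treatment-emergent AE twice: once by onset from the randomized treatment onward, as Protocol 8.12.5 does, and once with Screening Visit 1 as the reference point. SAP 13.2.3 adds: "The primary safety endpoint for this study is any severe device-related complication where relationship to the device was assessed by the clinical event committee". It plans Fisher's exact tests for device-related complications, although SAP 12.6 and Protocol 8.12.4 plan no inferential statistics for safety.

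**The concern.** For an SAE judged unrelated, one section forbids the entry and another requires it. If sites followed 5.15.1, a table headed as all SAEs would hold related SAEs only, within a shorter window, and nothing in the output would tell the reader so. An unrelated death might then appear only in the disposition summary under Protocol 8.8. No later analysis can restore events that were never entered.

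The two SAP issues are smaller but also affect what the safety tables mean. Under the second definition in SAP 12.7, an event in the run-in, before any randomized treatment, can count as treatment emergent. And a reader of SAP 13.2.3 would expect a tested primary safety endpoint that the endpoint sections do not contain.

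**Working it through.** There is no plan figure to reproduce. The check sets the rules side by side and runs cases through them.

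| Source | Relatedness condition | Start | End |
|---|---|---|---|
| Protocol 5.15.1, SAEs | ulcer, treatment or procedures | first randomized treatment | Treatment Visit Week 12 |
| Protocol 5.15.1, AEs | ulcer, treatment or procedures | SV2 | Treatment Visit Week 13, plus unscheduled visits |
| Protocol 5.15.5, eCRF list, SAEs | none | consent | last study visit |
| Protocol 5.15.5, special instructions (reporting to sponsor) | device or procedures; ulcer not named | not stated | not stated |
| Synopsis, Protocol 8.12.4, SAP 3.4 and 12.6 | none (all SAEs) | not stated | not stated |

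**Case 1: unrelated death in Week 6.** 5.15.1: not recorded. 5.15.5: recorded. Endpoint: counted.

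**Case 2: unrelated hospitalization in screening.** 5.15.1: excluded on relatedness and on time. 5.15.5: recorded.

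**Case 3: related SAE between SV2 and randomization.** It is outside the SAE window of 5.15.1. Since an SAE is defined there as a kind of AE, it could still enter through the wider AE window. This case is only partly lost.

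**Case 4: SAE three weeks after confirmed closure, ulcer first closed at TV13.** TV13 is nominally Day 84, confirmation is 7 days later and the follow-up visit 28 days after that: 84 + 7 + 28 = Day 119. Even if the 5.15.1 SAE window runs to Day 84, 119 − 84 = 35 nominal days of participation fall outside it. 5.15.5 covers them. An ulcer that closes early enough leaves no such gap.

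**Case 5: SAE attributed to the ulcer but not to device or procedures.** Both recording rules take it; the reporting rule does not require it. Because reporting is done on the AE eCRF, a site could take the reporting rule as a limit on what it enters.

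Cases 1, 2 and 4 show that data recorded under 5.15.1 fall short of the endpoint. Data recorded under 5.15.5 do not. Before treatment, the SAE gap under 5.15.1 applies to every randomized subject: nominally 14 days from SV1 (17 at most under the synopsis), plus any time between consent and SV1.

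**Treatment-emergent events.** The first limb of the second SAP 12.7 definition asks only that the event was absent at SV1 and is not a chronic condition from the history. It has no cut at the start of treatment. The run-in exposed to it for AEs is nominally 7 days (SV2 to TV1) under 5.15.1 and 0 under the AE item of 5.15.5, which starts after the first randomized treatment. For SAEs under 5.15.5 it is nominally 14 days (SV1 to TV1). An event in that interval is treatment emergent under one definition and not under the other. Such events precede randomized treatment, so counting them adds to both arms and pulls the rate ratio toward one.

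**SAP 13.2.3.** The endpoint named there is absent from the synopsis and from SAP 3.4. It speaks of severe complications and then tests serious ones, a distinction Protocol 5.15.2 insists on. Its Fisher tests contradict SAP 12.6.

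**The case against.** The strongest case on the other side is that related-only collection is a choice a sponsor can make for a cleared device, and that the documents could be reconciled toward it. Protocol 8.2.4 does not say all SAEs, and the reporting rule leans toward related events. This stands as to direction: narrowing the endpoint wording would also remove the contradiction. It does not remove the contradiction as written, because the synopsis, Protocol 8.12.4 and SAP 3.4 and 12.6 all promise every SAE.

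Several stronger readings are tempting and should not be drawn:

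- A reader might infer that AE collection was left out of the 4-week visit, because the list in Protocol 6.2.4 has no AE item. That section defers to Table 3, which marks adverse events at that visit.
- A reader might infer that the SAE window stops at TV12, because Protocol 6.2.1 calls the Day 7 visit Week 2, and a footnote to Table 3 labels the last treatment visit Week 13. Protocol 8.3 equates 12 weeks with 84 days and 8.6 ties Week 12 to TV13. The label should be clarified, but the argument here does not depend on it.
- A reader might infer that sites followed different rules, or that the loss favours one arm. The documents contain nothing on either.
- A reader might conclude that the missing events must be retrieved. That means going back through charts, including those of subjects who have left the study. In an open-label trial, late ascertainment can itself differ by arm.

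It is also fair that safety output is mainly descriptive, so the double definition in SAP 12.7 is a wording correction with an effect of unknown size.

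**Conclusion.** This is an internal contradiction in current text. Protocol 5.15.1 and 5.15.5 cannot both be followed for an unrelated SAE, and data recorded under 5.15.1 cannot yield the stated all-SAE endpoint. The consequence is conditional: if every site followed 5.15.5, the endpoint is met. If 5.15.1 was followed, the missing events are unrelated SAEs at any time, and SAEs before first treatment or in the follow-up of late closers, except related ones that fall within the wider AE window.

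The number of SAEs affected cannot be derived from the documents. No bias between arms is shown, and the primary efficacy analysis is unaffected. The matter should be fixed before final lock, on which SAP 11.1.1 bases the safety results. It concerns the whole safety population, which SAP 10.3 equates with the ITT population and to which the 3 March 2020 randomization cut-off for primary efficacy does not apply.

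The two SAP inconsistencies are real, separate and smaller.

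**What to change.** 1. Reconcile Protocol 5.15.1, the eCRF list in 5.15.5 and the special instructions for SAEs to one scope and one window with explicit start and end, consistent with the stated endpoint. A protocol wording change needs sponsor and IRB approval (Protocol 11).
2. Rewording does not change data already collected. Before final lock, document which rule was applied and label the SAE tables with it. If unrelated SAEs were not collected, title the tables related SAEs, give the window used, and do not call them all SAEs. This costs a footnote and a title.
3. A retrospective query for unrecorded SAEs is optional. It would reach up to 30 sites and fewer than 240 randomized subjects and would need chart review, so it is not clearly cheap. If made, it should be identical in both arms, and events found that way should be flagged as retrospective.
4. In SAP 12.7 keep one definition, in line with Protocol 8.12.5: an event that begins once randomized treatment has started, or a pre-existing event that worsens after that point. The reference point for worsening must move from SV1 to the first randomized treatment; otherwise an event that starts in the run-in and worsens on treatment would be lost.
5. In SAP 13.2.3 state whether the primary safety endpoint and the Fisher tests are retained, and align them with the synopsis, SAP 3.4, Protocol 8.12.4 and SAP 12.6. Items 4 and 5 cost SAP wording only.
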